Each assessment will include 1) questionnaires on sleep (ISI, PSQI, MEQ-SA), mood (POMS), anxiety (STAI), depression (CES-D), pain (BPI and VAS), fatigue (MFSI, BFI, FACIT-F), cognitive problems (FACIT-COG), exercise (Godin), symptoms (Symptom Inventory), sleep medications and stimulant use (medication and CAM Use forms), and quality of life (FACIT), 2) a daily diary for assessing sleep patterns and specific symptoms, 3) one week of actigraphy 4) physical function tests (6-minute walk and handgrip tests), 5) and a fasting blood draw. The actigraphs are small, water-resistant devices; one is worn around the wrist for 7 consecutive days to gather data on sleep and circadian rhythm. The other is worn on the waist for the same 7 consecutive days to determine physical activity. Participants will complete their questionnaires at the time of their assessments or at home.

- 6.14 **Requesting Actigraphs, Blood Draw Kits and Other Study Materials:** Study initiation materials will be shipped to the NCORP after the entire cohort is registered. These materials are comprised of 1) the coordinator's kit (including equipment for conducting the 6-minute walk test and handgrip test), 2) the video recorder, 3) actigraphs, 4) yoga kits, and 5) blood supplies. The study supplies will be shipped from the Research Base via FedEx for delivery within 2-3 business days.
- 6.15 **Baseline Assessments:** Baseline assessments will occur on Study Days -7 to -1, or during study week 1. The coordinator will charge and initialize the actigraphs. The actigraphs should be initialized no earlier than the Wednesday prior to baseline week to ensure adequate data storage. The coordinator will also instruct all participants on how to put each actigraph on and give them written instructions. An actigraph manual along with videos and training sessions are provided for coordinators by the Research Base. The coordinator will reinforce with the participant to wear their actigraphs for 7 consecutive days and to begin filling out their daily diaries on day -7. Only NCORP site staff who have completed the URCC YOCAS® study actigraphy training can instruct participants on how to wear them and give them to participants.

All participants will be asked to complete on study data and clinical information forms as well as a series of questionnaires to evaluate insomnia, their emotional state, and their physical health. The questionnaires will take

approximately 35 minutes to complete and participants are asked to complete them as close to the end of the baseline week as possible. Treatment notes including all cancer-related treatment should be submitted with this assessment. A 6 minute walk and handgrip test will be conducted to measure strength, and a fasting (minimum of 8 hours) blood draw of approximately 3 tablespoons, will be completed to assess inflammation. Coordinators will call participants to remind them to wear the actigraphs and complete study assessments on the Thursday or Friday prior to the start of the baseline assessment. At the end of the baseline week, a second call is made to remind participants to complete study assessments and to inform them of their study randomization assignment. Alternatively, these reminders can be made in person at the baseline assessment visit. Study coordinators are to inform participants of their study randomization after fitness testing, fasting blood draw and case report forms have been completed. Only NCORP site staff who have completed the URCC Research Base training on functional assessment and blood draw and processing are allowed to perform these assessments and process the blood specimens.

- 6.16 **Intervention:** Participants will begin the intervention immediately after baseline assessments are complete. Participant adherence will be monitored by attendance records, daily diaries, and actigraphy.
- 6.16.1 Participants in the YOCAS® and health education groups will partake in the intervention twice a week for 75 minutes over a 4 week period (study days 0-27 or study weeks 2-5).
- 6.16.2 Participants in the CBT-I group will complete one session a week for 90 minutes over an 8 week period (study days 0-55 or study weeks 2-9).
- 6.17 **Mid-Point Assessment:** Half-way through the intervention, participants will again complete study questionnaires (as detailed in section 6.13 above) as well as the 6 minute walk and handgrip tests, fasting blood draw, 7 more consecutive days of wearing the actigraphs, and continue recording in their daily diaries. The coordinator will call and remind the participants to wear their actigraphs for 7 consecutive days, to continue filling out their daily diaries, and to complete all study assessments.
- 6.17.1 For participants in the YOCAS® and health education groups, the mid-point assessment will be done during study days 7-13 or study week 3.
- 6.17.2 For participants in the CBT-I group, the mid-point assessment will be done during study days 21-27 or study week 5.
- 6.18 **Post-Intervention:** At the end of the intervention period, participants will complete all study procedures as outlined above and stop entering data in their daily diaries after this assessment. The coordinator will call participants and remind them to wear the actigraphs, complete forms and diaries, and to complete all study assessments.
- 6.18.1 For participants in the YOCAS® and health education groups, the post assessment will be done during study days 21-27 or study week 5.
- 6.18.2 For participants in the CBT-I group, the post assessment will be done during study days 49-55 or study week 9.
- 6.19 **3-Month Post Intervention Follow Up:** At this assessment, participants will again be asked to fill out questionnaires, complete a 6 minute walk and a handgrip test, a fasting blood draw, 7 consecutive days wearing the actigraphs, and filling out daily diaries for that time. The coordinator will complete a scheduling and reminder call during the week prior to the follow-up visit.
- 6.19.1 For participants in the YOCAS® and health education groups, the 3-month post assessment will be done during study week 17.
- 6.19.2 For participants in the CBT-I group, the 3-month post assessment will be done during study week 21.
- 6.20 **6-Month Post Intervention Follow Up:** At this assessment, participants will again be asked to fill out questionnaires, complete a 6 minute walk, and a handgrip test, a fasting blood draw, 7 consecutive days wearing the actigraphs, and filling out daily diaries for that time. Additionally, participants will complete a feedback form

and a 15-minute qualitative exit interview at the end of the 6-month post-intervention assessment period. All participants will be debriefed and the 3 study arms will be explained. The coordinator completes a scheduling and reminder call during the week prior to the follow-up visit.

6.20.1 For participants in the YOCAS® and health education groups, the 6-month post assessment will be given during study week 29.

6.20.2 For participants in the CBT-I group, the 6-month post assessment will be given during study week 33.

6.21 **Management of actigraphy:** Actigraphy will be handled by the PEAK Laboratory at the Research Base.

6.21.1 Each NCORP site will be responsible for designating someone on the research staff to be responsible for receiving the actigraphs and an alternate person to cover in case of vacation or illness. The staff member will verify identification numbers on the actigraphs and log all equipment onto the Investigational Device Accountability Record. This form will be used to track actigraphs arriving from the URCC, actigraphs given to participants, actigraphs returned from participants, and actigraphs returned to the URCC. Recording the identification codes on the devices as assigned to each participant will ensure that the same actigraphs are used for each participant.

6.21.2 When the NCORP site notifies the Research Base that the entire cohort has been registered, the actigraphs will be shipped from URCC fully charged. The coordinator will recharge them and initialize each actigraph. The actigraphs should be initialized no earlier than the Wednesday prior to baseline week to ensure adequate data storage. The coordinator will instruct each participant on how to put the actigraphs on, care for them and charge them. The coordinator will also give them written instructions developed by URCC, and successfully used in prior studies to aid in proper data acquisition.

6.21.3 The Research Base PEAK Lab staff will ensure that the actigraphs are in good working order before shipping the units to the NCORP site. The NCORP site staff will distribute the actigraphs, actigraph chargers and actigraph instructions to each participant at the baseline assessment. The participants must have the actigraphs and must be able to start wearing them when they get up on the morning of Study Day -7 (Sunday morning). Participants will wear a wrist actigraph 24 hours a day for 7 consecutive days, and a second actigraph will be worn around the participant's waist 24 hours a day for the same 7 consecutive days. The coordinator will instruct the participant when to remove the actigraphs (the following Sunday). Both will be worn during the baseline assessment, the mid-point assessment, the post-intervention assessment, the 3-month post intervention follow-up, and the 6-month post intervention follow up. As the actigraphs are water resistant but not waterproof, participants will take the actigraphs off only when they shower, bathe, swim or do anything where the actigraphs would be submerged in water. Otherwise, they should wear them as described above during each assessment period.

6.21.3.1 NCORP research staff will explain to participants the procedures for wearing the actigraphs and reinforce the importance of wearing them through the night.

6.21.3.2 All study participants will keep both actigraphs from baseline throughout study week 5 (this is the post-intervention assessment period for yoga and health education groups, and mid-point for CBT-I group). All actigraphs will then need to be retrieved from participants during study week 6. All data needs to be downloaded and sent to URCC. **DO NOT RE-INITIALIZE ANY ACTIGRAPHS UNTIL CONFIRMATION IS RECEIVED THAT URCC HAS THE DATA.** Once it is confirmed the data has been properly downloaded the actigraphs can be reinitialized.

The coordinator will need to make arrangements within 3 business days following baseline assessments to meet one participant in each arm and download their actigraph data to be submitted to URCC for the data quality audit at the beginning of the cohort and return the actigraphs to the 3 participants prior to the mid-point assessment.

The coordinator will need to re-initialize and return the actigraphs to participants in the CBT-I group only, during study week 8, so they can wear them for post-intervention assessments during study week 9.

The coordinator will need to re-initialize and return the actigraphs to participants in all three study groups for both the 3-month and 6-month follow-up assessments. Actigraphs need to be sent to participants during the week prior to the scheduled 3- and 6-month follow-ups.

When not wearing the actigraphs, participants are instructed to plug them into the wall chargers and keep them charging. Every attempt will be made to send the same actigraphs to participants for all assessments.

6.21.3.3 The NCORP research staff will download the data from the actigraphs within 3-4 business days of receiving them from the participants and upload them to the URCC NCORP Research Base secure website. **DO NOT RE-INITIALIZE ANY ACTIGRAPHS UNTIL CONFIRMATION IS RECEIVED THAT URCC HAS THE DATA.** The electronic data file will be saved in a privacy-secure electronic file at the Research Base and PEAK Human Performance Laboratory. In the event the supply of actigraphs is ample, the Research Base may allow the NCORP to keep devices between the post-intervention and the 2 follow-up assessments. This will be determined on a case by case basis.

6.21.4 **Assessment Training and Adherence to Assessment Protocols:** The University of Rochester PEAK Human Performance Laboratory, a URMC CTSI Clinical Research Core Lab, provides services to aid investigators in effectively implementing behavioral interventions and assessing clinical outcomes that involve physical activity and function. The PEAK Lab has been instrumental in standardizing the procedures for the collection of actigraphy, handgrip, and 6-minute walk data to ensure adherence to protocol. The staff is also adept at training NCORP site staff to properly collect, process, store and ship blood for NCORP studies. Study Chair, [name], directs the PEAK Lab which has been closely involved in URCC Research Base studies since its inception. PEAK Lab staff have designed support materials and trained NCORP site staff to administer the behavioral interventions and outcome assessments for the URCC studies involving yoga (U3905), EXCAP intervention (UCCO08106) and many other URCC Research Base studies. The PEAK lab staff are adept at managing and analyzing actigraph data and all functional data for NCORP Research Base studies as well as biological samples.

The URCC also requires each NCORP staff member to go through training programs which includes, overall protocol information, functional and clinical assessments, actigraphy, blood collection and processing, videotaping, proper forms completion, and quality control checks. Refresher training will be provided as needed.

Adherence will be monitored throughout the study as the information is received at the URCC. We have specifically implemented an extra quality assurance check after baseline, as well as having the NCORPs videotape the 3rd intervention class to monitor instructor adherence to the specific program they are to teach.

6.22 **Participant Reimbursement:** Participants will receive a \$50.00 reimbursement for their time and effort to complete each study assessment for a total reimbursement of \$250.00. Participants are only reimbursed for the study assessments they actually complete. Each NCORP will be responsible for dispersing the reimbursements to study participants using methods appropriate for their sites. Each NCORP will invoice the URCC Research Base monthly for reimbursement expenses. URCC will only reimburse for the cash value of \$50.00 per assessment; no gift card or other fees will be reimbursed if NCORPs choose to use methods of reimbursement that incur extra fees in lieu of cash. Send invoices to: [name], [name] [[name]](mailto:[contact])

6.23 **Adverse Events:**

6.23.1 Risks from participating in this research:

- YOCAS® may result in muscle soreness, strains, and/or joint pain.
- CBT-I may result in temporary increases in daytime fatigue, sleepiness, and memory and concentration difficulties.
- Participants may feel upset or worried when filling out the questionnaires.
- Drawing blood may cause pain and bruising at the site where the blood is taken, and sometimes, may cause people to feel light-headed or even to faint. Rarely, you might get an infection at the site of the needle stick.

6.23.2 Adverse events will be reported using the URCC Adverse Event form. This form can be found on the URCC NCORP Research Base website.

	Grade 1	Grade 2			Grade 3				Grade 4		Grade 5	
	Unexpected and Expected	Unexpected		Expected	Unexpected		Expected		Unexpected	Expected	Unexpected	Expected
		with hospitalization	without hospitalization		with hospitalization	without hospitalization	with hospitalization	without hospitalization				
Unrelated Unlikely	Not Required	Not Required	Not Required	Not Required	Not Required	Not Required	Not Required	Not Required	10 Calendar Days	Not Required	10 Calendar Days	10 Calendar Days
Possible Probable Definite	Not Required	10 Calendar Days	Not Required	Not Required	10 Calendar Days	10 Calendar Days	Not Required	Not Required	24-Hour; 5 Calendar Days	10 Calendar Days	24-Hour; 5 Calendar Days	10 Calendar Days

Hospitalization is defined as initial hospitalization or prolongation of hospitalization for  $\geq 24$  hours, due to adverse event.

6.23.3 Submit written adverse event reports in one of the following ways:

(1) PDF by email: [[name]](mailto:[contact])

(2) By mail: [name]  
URCC NCORP Research Base  
[name]  
[name]  
[name]  
[name]

(3) By fax: [name]  
[contact]

6.23.4 CTCAE term (AE description) and grade: The descriptions and grading scales found in the revised NCI Common Terminology Criteria for Adverse Events (CTCAE) version 4.0 will be utilized until March 31, 2018 for AE reporting. CTCAE version 5.0 will be utilized for AE reporting beginning April 1, 2018. All appropriate treatment areas should have access to a copy of the CTCAE version 5.0. A copy of the CTCAE version 5.0 can be downloaded from the CTEP web site [http://ctep.cancer.gov/protocolDevelopment/electronic\\_applications/ctc.htm](http://ctep.cancer.gov/protocolDevelopment/electronic_applications/ctc.htm).

6.23.5 An *unexpected* adverse event is defined as any adverse experience, the specificity or severity of which is not consistent with the risk information described in section 6.23.1.

6.23.6 A serious event refers to any event in which the outcome results in any of the following: death, a life-threatening adverse experience, inpatient hospitalization or prolongation of existing hospitalization, a persistent or significant disability, incapacity, or a congenital anomaly/birth defect. Important medical events that may not result in death, be life-threatening, or require hospitalization may be considered a serious adverse drug experience when, based upon appropriate medical judgment, they may jeopardize the participant and may require medical or surgical intervention to prevent one of the outcomes listed in this definition.

6.23.7 Adverse events should be reported to the local IRB as per its requirements.

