5.3.7.8 Stratification: ISI severity screening score and current hormone therapy status (yes/no)

5.4 An email confirmation of registration will be sent from the URCC NCORP Research Base.

5.5 Registration and randomization of participants will occur when an entire cohort has been consented. A cohort consists of a yoga group, a CBT-I group and a health education group at a single NCORP location. All participants are registered at the same time. The minimum number of participants to comprise a cohort is 15 and the maximum is 30. The NCORP must notify the URCC when the final participant in a cohort is being consented, and provide the total number of participants enrolled to that cohort, the institution's CTEP ID, and the date of the first day of the baseline week. The Research Base requires a 24-hour turn-around time to open the registration site. The NCORP site must then register the entire cohort of participants within 24 hours and will receive the randomization assignment for each participant at that time. **NCORP coordinators will know the randomization assignments; however participants are not to be notified of their randomization assignments until they have completed all baseline assessments.** The participants randomized to each of the three conditions will all participate in the intervention they are assigned together as a group and the sessions will only contain study participants. (Note: The URCC has successfully used this method of randomization in previous studies including U3905 (the prior yoga study), U2991 and U9994 where cohorts were randomized to treatments delivered using group formats.) Participant cohorts will be recruited at each NCORP and then randomized; this will allow for statistical analyses by site.

- 5.6 A total enrollment of 720 participants (accounting for 30% of participants providing non-evaluable data) is planned as follows:

Group	N	Evaluable
YOCAS	240	168
CBT-I	240	168
Health Education	240	168

- 5.7 Randomization will be stratified by ISI severity score obtained during the screening process (ISI score of 10-18 = “moderate” and 19-28 = “severe”) and hormone therapy (two levels: yes/no). In addition, participant cohorts will be recruited at each NCORP and then randomized; this will, in turn, allow for statistical analyses by site.
- 5.8 The three study arms are as follows:
- Arm 1 = The standard YOCAS® intervention  

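### Section 6.15 uses one call both to chase unfinished baseline forms and to disclose the arm, against the plan's own sequence rule and with no completion check to protect the baseline ISI covariate

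*Combined protocol and SAP*

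**What the plan says.** Section 5.5 has a site register its whole cohort at once; the site "will receive the randomization assignment for each participant at that time". It adds that "NCORP coordinators will know the randomization assignments", but that "participants are not to be notified of their randomization assignments until they have completed all baseline assessments". Under section 6.14, "Study initiation materials will be shipped to the NCORP after the entire cohort is registered". The site therefore holds the assignments before the baseline tests can begin.

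Section 6.15 places baseline on Study Days -7 to -1. On the questionnaires it says that "participants are asked to complete them as close to the end of the baseline week as possible", and section 6.13 says "Participants will complete their questionnaires at the time of their assessments or at home". At the end of that week, "a second call is made to remind participants to complete study assessments and to inform them of their study randomization assignment". The reminders may instead be given in person at the baseline visit. The section then states the intended order: "Study coordinators are to inform participants of their study randomization after fitness testing, fasting blood draw and case report forms have been completed".

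Section 10.7.1 makes post-treatment ISI the response in the primary model, with group and baseline ISI as fixed effects and site as a random effect.

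**The concern.** A reminder to complete assessments presupposes that some are outstanding. If the same call also gives the arm, a participant with forms still at home can answer the baseline ISI already knowing the allocation. The timing makes this plausible, because the forms are meant to be done late in the week and the call comes at its end. The in-person alternative has the same gap when questionnaires are taken home from the visit.

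A baseline covariate protects the treatment comparison because allocation cannot influence it. If knowing the arm moves the reported baseline differently between arms, the ANCOVA adjusts for a difference that allocation created and carries part of it into the estimated effect. The non-inferiority margin is only 1.15 ISI points, so there is little room for such a bias.

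**Working it through.** **Setting the instructions side by side.** The two sequence rules do not match each other. Section 5.5 requires all baseline assessments to be complete. Section 6.15 lists fitness testing, blood draw and case report forms. Actigraphs come off only on the following Sunday (section 6.21.3), so a disclosure before then could satisfy 6.15 and break 5.5. Neither rule is backed by a check. The section 11.0 table records a call log, with a second call at the end of baseline, but no confirmation that forms are complete. The data quality check in section 6.8.1 covers one participant per arm and is due by the third work day after baseline, so it does not control when the arm is disclosed.

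**Inputs** (sections 10.1, 10.2.1 and 10.7.1): SD 4.6; baseline-to-post correlation 0.576; 168 evaluable per arm; margin 1.15; one-sided alpha 0.025; 30% non-evaluable.

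**The plan's own figure.**
- Residual SD = 4.6 × √(1 − 0.576²) = 3.760.
- SE of the difference = 3.760 × √(2/168) = 0.410.
- Power at a true difference of 0 = Φ(1.15/0.4103 − 1.96) = 0.80.
- Enrolment = 168/0.70 = 240 per arm, 720 in total.

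The stated sample size and power reproduce.

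**Effect of a shift in the covariate.** The adjusted difference is the difference in post-treatment means minus slope × the difference in baseline means. With equal pre and post SDs (an assumption), the slope equals the correlation, 0.576. A disclosure-induced difference d between arms in mean reported baseline ISI then gives a bias of 0.576 × d. If d raises the YOCAS baseline relative to CBT-I, the bias favours YOCAS. If it lowers it, the bias goes against YOCAS.

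- Power if the bias is against YOCAS (true difference 0) = Φ((1.15 − 0.576d)/0.4103 − 1.96).
- False non-inferiority if it favours YOCAS (true difference at the margin) = Φ(0.576d/0.4103 − 1.96).

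| d (assumed) | Bias | Share of margin | Power, bias against | False non-inferiority, bias in favour |
|---|---|---|---|---|
| 0 | 0 | 0% | 80% | 2.5% |
| 0.1 | 0.06 | 5% | 76% | 3.4% |
| 0.25 | 0.14 | 13% | 69% | 5.4% |
| 0.5 | 0.29 | 25% | 56% | 10.4% |

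**What d means.** It is an arm-wide mean: d = f × δ, where f is the fraction answering after disclosure and δ is the difference in reporting between such participants in the two arms. The documents give neither. With f = 10% and δ = 1 point, d = 0.1. To reach d = 0.5 takes δ = 2.5 points at f = 20%, or 5 points at f = 10%. Section 10.2.1 calls 2.3 points nontrivial, so d = 0.5 sits at the high end.

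**The case against.** The strongest reply is that the plan states the right order twice, and that a careful coordinator can follow every sentence by reminding, confirming completion and only then disclosing. On that view an ISI answered after disclosure is a deviation and not the planned procedure. This stands, and it limits the point to an instruction that invites the deviation and a missing check. It does not remove the point: the call is the operational step that sites will follow, completion at home cannot be seen over the telephone, and nothing requires confirmation first.

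It is also fair to say that section 6.2 has participants told that all three arms are interventions for sleep. That weakens the reason to expect different re-rating between YOCAS and CBT-I, though it does not exclude it. No direction can be given.

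A reader might infer three stronger things that the documents do not support:
- That participants learn their arm before baseline by design. Early release is to sites only; section 5.5 forbids telling participants.
- That coordinators' knowledge of the arm biases the primary analysis directly. The ISI is self-reported (section 7.3.1). The walk and grip tests that coordinators run feed exploratory aims only (section 3.3).
- That the plan leaves randomised participants without a baseline ISI unaddressed. Section 10.1 allows for 30% non-evaluable and counts the baseline ISI in that definition, and section 10.6.2 provides multiple imputation under missing at random.

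**Conclusion.** The point holds as a conflict between instructions and an unguarded covariate. The dual-purpose call in section 6.15 does not sit with the disclosure rules in 5.5 and 6.15, and no completion check resolves it. If the stated order is kept, the bias is zero. If some participants answer the baseline ISI after disclosure, the adjusted difference moves by about 0.576 × d. That is 0.06 points at d = 0.1 and 0.29 points, a quarter of the margin, at d = 0.5.

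These figures rest on equal pre and post SDs, the plan's SD and correlation, and assumed values of d. They show sensitivity and do not predict what will happen. In particular, 56% power or 10.4% false non-inferiority should not be read as the expected consequence. The 168 per arm and 720 total are unaffected. The correction is still worth making, because it protects the primary covariate at almost no cost.

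**What to change.** Reword section 6.15 so that the end-of-week contact is a reminder only. Disclose the arm in a later step, once the coordinator has logged dated receipt of the baseline ISI and other questionnaires, the walk test, the grip test and the blood draw. Apply the same order when reminders are given in person, so that questionnaires taken home are back before the arm is disclosed. Align section 5.5 with the same list, so that the two sections name the same conditions and say whether the last day of actigraph wear is among them.

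The cost is one extra short contact for participants whose forms are outstanding, and one more dated entry in the site's records. It is not necessary to make the Research Base withhold the cohort's assignment list until all baseline work is done. Actigraphs come off on the Sunday and the intervention starts on Day 0, which would leave almost no time to place 15 to 30 people in three groups.

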#### 6.24 **Data Safety and Monitoring:**

6.24.1 All adverse events requiring reporting will be submitted to [name] as described above. Adverse events that are *serious AND unexpected AND related* will be forwarded to the study chair and the URCC Data Safety and Monitoring Committee (DSMC) chair immediately upon receipt at URCC. Additional information may be requested upon their review.

6.24.2 All adverse events reported to URCC are entered into a protocol-specific spreadsheet. Adverse event rates are monitored utilizing the spreadsheet. If a serious adverse event is being reported frequently, the study chair will conduct a detailed review. The DSMC chair will be notified and will determine if further action is required.

6.24.3 The URCC Data Safety Monitoring Committee (DSMC) will review study progress and cumulative reports of adverse events at annual meetings. An overall assessment of accrual and adverse events will enable the committee members to assess whether significant benefits or risks are occurring that would warrant study closure.

6.24.4 The URCC will notify the NCORPs immediately of any serious safety concerns identified by the DSMC. DSMC reports will be available for download on the Research Base website.

---

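### The adverse-event reporting grid and the serious-event definition do not match, so some related serious events are not required to be reported to URCC

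*Combined protocol and SAP*

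**What the plan says.** Four parts of sections 6.23 and 6.24 bear on this.

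- **Seriousness (6.23.6).** The definition opens: "A serious event refers to any event in which the outcome results in any of the following: death, a life-threatening adverse experience, inpatient hospitalization". Apart from death and threat to life, the qualifying outcomes include "inpatient hospitalization or prolongation of existing hospitalization, a persistent or significant disability, incapacity, or a congenital anomaly/birth defect". No minimum stay is set. The section adds: "Important medical events that may not result in death, be life-threatening, or require hospitalization may be considered a serious adverse drug experience".
- **What sites must submit (grid in 6.23.2).** The rows are attribution; the columns are grade, expectedness and, for some grades, hospitalization. The related row opens: "Possible Probable Definite Not Required 10 Calendar Days Not Required Not Required 10 Calendar Days 10 Calendar Days Not Required Not Required". The footnote begins "Hospitalization is defined as initial hospitalization or prolongation of hospitalization for" and sets a minimum of 24 hours.
- **Expectedness (6.23.5).** An event is unexpected if it is one "the specificity or severity of which is not consistent with the risk information described in section 6.23.1". Section 6.23.1 lists the risks in words (for example strains, temporary sleepiness, fainting at a blood draw) and gives no CTCAE grade.
- **What happens centrally (6.24).** Under 6.24.1, events that require reporting are submitted, and those that are serious, unexpected and related "will be forwarded to the study chair and the URCC Data Safety and Monitoring Committee (DSMC) chair immediately upon receipt at URCC". Under 6.24.2, events reported to URCC go into a spreadsheet from which rates are monitored: "If a serious adverse event is being reported frequently, the study chair will conduct a detailed review". Under 6.24.3 the DSMC reviews cumulative adverse-event reports each year.

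The only other route given is to the local IRB (6.23.7). The records table in section 11.0 lists no adverse-event form.

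**The concern.** Submission depends on one set of attributes, and central action depends on another. The study chair and the DSMC act on seriousness, but they see only what the grid sends them. Where the grid exempts an event that 6.23.6 calls serious, a site can follow the plan exactly and the central safety review still does not count the event.

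The review most exposed is 6.24.2. Section 6.24.1 deals only with unexpected events. The frequency check in 6.24.2 has no expectedness condition, so it is the natural place to notice an expected serious harm that occurs too often. The grid leaves some of those events out. The annual DSMC review in 6.24.3, which is meant to judge whether risks warrant closing the study, draws on the same reports.

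**Working it through.** The plan states no figure on this point, so the check is a comparison of the grid with the definitions.

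**Does the extracted grid align?** The headings give 1 column for Grade 1, 3 for Grade 2, 4 for Grade 3, 2 for Grade 4 and 2 for Grade 5: 1 + 3 + 4 + 2 + 2 = 12. Each attribution row has 12 entries, so the cells can be assigned without guesswork.

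**Related row (possible, probable or definite), cell by cell:**

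| Grade | Expectedness | Hospitalization (24 h or more) | Report |
|---|---|---|---|
| 1 | either | not split | Not required |
| 2 | unexpected | with | 10 calendar days |
| 2 | unexpected | without | Not required |
| 2 | expected | not split | Not required |
| 3 | unexpected | with | 10 calendar days |
| 3 | unexpected | without | 10 calendar days |
| 3 | expected | with | Not required |
| 3 | expected | without | Not required |
| 4 | unexpected | not split | 24 hours; 5 calendar days |
| 4 | expected | not split | 10 calendar days |
| 5 | unexpected | not split | 24 hours; 5 calendar days |
| 5 | expected | not split | 10 calendar days |

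Five of the 12 cells require no report. Three of them matter most when set against 6.23.6.

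1. **Expected Grade 3 with hospitalization.** An inpatient stay of 24 hours or more is serious under 6.23.6 on its face. The grid has a separate column for this case and exempts it, even when it is related.
2. **Expected Grade 2.** There is no hospitalization split, so an admitted case is exempt together with the others.
3. **Unexpected Grade 2 without hospitalization.** Because of the footnote, this cell includes inpatient stays shorter than 24 hours, which 6.23.6 counts as serious. It also includes a disability, or an important medical event judged serious. Such a case is serious, unexpected and related, which is the condition for forwarding in 6.24.1. Forwarding starts on receipt at URCC, and receipt is not required.

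Cells 1 and 2 concern expected events. They fall outside 6.24.1 and affect only the reviews in 6.24.2 and 6.24.3. Cell 3 is the only one of the three that conflicts with 6.24.1 itself.

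**Expectedness.** Take a related Grade 3 strain that leads to admission. If the site reads strain as a listed risk, the event is expected and no report is required. If the site judges its severity inconsistent with 6.23.1, the event is unexpected, is due within 10 calendar days and, being serious, is forwarded. The text of 6.23.1 and 6.23.5 does not settle which reading applies, so two sites can treat the same event differently.

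**The case against.** The best defence is that 6.23.5 already repairs most of the gap. The listed risks read as mild: soreness, temporary fatigue, feeling light-headed or fainting. None mentions admission. An admitted Grade 3 event could readily be judged unexpected by severity, and it would then be reportable and forwarded. A grid scaled to attribution and expectedness is also a defensible, proportionate choice. Related unexpected Grade 3 events, and all related Grade 4 and 5 events, are covered.

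Part of this stands. Reclassification will capture some events. It is not dependable, because 6.23.1 sets no grade at which a listed risk stops being expected. If every admitted Grade 3 event were meant to be unexpected, the grid's column for expected Grade 3 events with hospitalization would have no use.

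A reader might infer more than the documents support:

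- **That these events never reach URCC, or yield no reports at all.** An entry that no report is required does not forbid one; a site may report voluntarily.
- **That the planned number of fasting blood draws measures the problem.** It is a count of exposures. The documents give no rate of admission after a draw.
- **That no single site could see a cluster.** The number of sites is not stated, and nothing prevents one site from running several cohorts.
- **That the exemptions for unrelated events add to the defect.** Those events cannot meet the relatedness condition in 6.24.1.

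The documents also suggest low frequency in one arm: the earlier 410-participant trial of the same yoga program reported no study-related adverse events (section 2.0). That does not cover CBT-I or the blood draws.

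**Conclusion.** The concern holds as a mismatch between stated rules. Under the plan as written, related serious events that are expected and of Grade 2, or of Grade 3 with hospitalization, are not required to reach URCC. They can therefore be absent from the frequency review and from the DSMC's cumulative review. A narrow set of unexpected Grade 2 events meets the forwarding condition in 6.24.1 and is likewise not required to be submitted. These should be uncommon, since they need a stay under 24 hours, a disability, or a discretionary judgement that the event is medically important.

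The size can be given only in cells of the grid, not in events. The conclusion assumes that sites apply the grid literally and that no separate serious-event procedure exists outside the document; none is described in it. No endpoint, treatment estimate or power figure is affected. The point should be corrected because it weakens safety monitoring, but it does not undermine the trial's main analysis.

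**What to change.** Reconcile the grid in 6.23.2, the definitions in 6.23.5 and 6.23.6, and the monitoring rules in 6.24:

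1. Require a report to URCC, within the grid's existing timelines, for any event that meets 6.23.6 and is possibly, probably or definitely related, whatever its grade or expectedness.
2. Use one definition of hospitalization in the grid footnote and in 6.23.6.
3. State in 6.23.1 the severity up to which each listed risk counts as expected, so that 6.23.5 can be applied in the same way at every site. The sponsor should set those levels.

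The cost is a wording change, a revised grid and a few more adverse-event forms from sites. No visits or assessments are added.
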